Diagnosis and main criteria for inclusion	
 ▪ Men or women aged 18 years and older, inclusive ▪ Systemic Sclerosis as defined by 2013 the American College of Rheumatology (ACR) / European League Against Rheumatism (EULAR) classification. ▪ Steady daily doses of any immunosuppressive medication, vasodilators, antidepressants and anxiolytic use for 4 weeks prior to baseline. ▪ PROMIS-fatigue score of at least 45 ▪ Currently owns and operates a smart phone regularly ▪ Ability to provide informed consent
Study Design	Open label, single-arm, single center US study
Type of control	None
Number of participants	30
Primary outcome variable	Change in the PROMIS-Fatigue scale at four weeks

30

Plan for statistical analysis

The planned sample size of 30 SSc participants is based on practical considerations to obtain estimates of the magnitude of treatment differences for efficacy and safety rather than a desired power for a pre-specified difference.

From similar studies on Rheumatoid Arthritis and Systemic Lupus Erythematosus, the improvement of T-score after treatment is about 5. The standard deviation for general population is 10. However, we are restricting our population to participants with fatigue T-scores of less than 54 (with low score indicating high fatigue). With the range of T-score reduced about half, we expect the standard deviation to be about 5. The effect size is expected to be 1 (5/5).

Using paired t-test, we have 86% power to detect the effect size of 1 when we recruit 30 patients at a significance level of 0.05. We asked the IRB for the option of increasing the number of patients to 40, which will give us about 81% power to detect a smaller effect size of 0.8 at a significance level of 0.05.

Descriptive statistics will be derived for all clinical variables, mean and standard deviation for continuous outcomes and percentages for categorical and dichotomous variables.

The primary outcome of interest is fatigue, as measured by the FACIT-Fatigue. We will compare the mean change from baseline and four weeks in a repeated measures model.

The p-values resulting from formal statistical tests will be interpreted from a hypothesis-generating, rather than a confirmatory framework.

Table of contents

1. Introduction	9
1.1 Background	9
1.1.1 Scleroderma (systemic sclerosis).....	9

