4. STUDY DESIGN

4.1 Design overview

This clinical trial is a single-center, open-label, single-arm study of 30 individuals with SSc and fatigue.

The study will allow for subjects to continue standard of care medications for the management of SSc as background therapy.

The study design consists of a single, four-week intervention. The screening and baseline visits can be combined when the screening is not able to be performed over the phone in advance.

- **Screening phase:** up to 4 weeks prior to baseline visit
- **Observation period:** During this one week phase participants will track their daily Raynaud attack frequency and duration using a diary. This will occur in the seven days preceding the baseline intervention phase.
- **Open-label intervention phase:** This consists of a four-week period during which participants will use the Apollo wearable system as needed to manage symptoms including fatigue. During the intervention phase participants may use the wearable at their discretion and control. Participants will track their daily Raynaud attack frequency and duration using a diary during week 4 of Apollo use. Participants will complete questionnaires on day 1 of the open-label and intervention phase, and at their follow-up four weeks later.

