4.1.2 Intervention Phase

At the baseline visit, participants who have met all of the inclusion criteria. At this visit they will complete the following questionnaires:

- 1) PROMIS-fatigue
- 2) PROMIS-29
- 3) The QUIDS-SR
- 4) HAQ-DQ with SHAQ
- 5) Raynaud condition score, Raynaud visual analog scale and digital ulcer visual analog scale

They will then be provided the wearable Apollo system device. They will download the mobile application, and be taught how to install it and use it to control the wearable Apollo device by the research coordinator(s). Any questions will be answered at this time. Participants will be able to use the device from the time they leave the visit. Use of the device will be entirely at the subject's control.

In the week prior to their end-of-study visit, participants will complete a daily diary collection of Raynaud attack episodes and symptoms using the paper diary form. This will be provided prior to leaving the baseline visit.

Participants will be sent a reminder call or text the day before and day they are to begin their diary collection on one week prior to their scheduled end-of-study visit.

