6.2 Treatment assignment

This is an open-label, single-arm trial. No randomization or blinding will occur.

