8.1 General considerations

This section presents a summary of the planned statistical analyses. A statistical analysis plan (SAP) will be written for the study that contains detailed descriptions of the analyses to be performed. The SAP will be finalized prior to unblinding of the data.

Continuous variables will be summarized using descriptive statistics including n, mean, median, standard deviation, range (e.g., minimum and maximum). Qualitative variables will be summarized using counts and percentages. Graphical methods will be used in this pilot study to assess the pattern of response over time for key variables and to assess the relationships among variables.

Unless otherwise specified, statistical analyses will be performed using SAS Version 9 or higher. Where appropriate, statistical tests will be conducted at the 0.05 significance level (with no adjustments for multiplicity) using two-tailed tests and p-values will be reported.

Given the rare nature of SSc and the consequent small sample size for this pilot study, the statistical power of any comparisons is limited (i.e., there is sufficient power to detect only large treatment differences). As such the analysis will be largely descriptive in nature. The p-values resulting from formal statistical tests will be interpreted from a hypothesis-generating, rather than a confirmatory framework.

Analysis sets

As this is an open-label study, all participant who have used the Apollo system wearable for at least one dose (one day) will be analyzed. The primary endpoint and all secondary outcomes will be assessed using this analysis set.

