8.2.2 Efficacy

The primary endpoint is the mean change from baseline to end of the two-week intervention in the PROMIS-Fatigue questionnaire. For the primary analysis, changes in score will be compared in the two treatment groups using an repeated measures t-test. If the assumptions of this parametric model are not met, an alternative non-parametric model will be used. This model is based on the extension of the Wilcoxon rank-sum test to allow for covariate adjustment (9). This rank ANCOVA can provide additional power associated with baseline covariate adjustment, even when the outcome variable is not normally distributed 1(10).

Analysis for secondary outcome measures that are continuous will be performed using a similar approach as that for the primary endpoint. We will compare the change in each secondary outcome measure from baseline to week 2 using an ANCOVA model or its non-parametric counterpart if the model assumptions aren't met. Analyses of secondary outcomes measures that are discrete will be performed using Fisher's exact tests. Analyses of secondary outcome measure that are counts will be performed using Poisson regression.

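### Section 8.2.2 replaces the test of mean change with a rank method on an undefined trigger and keeps no mean-based test; the named fallback cannot be run in one arm, and its natural one-sample form would not test the stated endpoint if changes are skewed

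*Combined protocol and SAP*

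**What the plan says.** Section 8.2.2 states the target: "The primary endpoint is the mean change from baseline to end" of the intervention on the PROMIS-Fatigue questionnaire, tested with a repeated measures t-test. It then adds "If the assumptions of this parametric model are not met, an alternative non-parametric model will be used". The replacement is described as an extension of the Wilcoxon rank-sum test that allows covariate adjustment, that is, a rank ANCOVA. The section does not say how the assumptions are checked, what threshold applies or who decides. It does not say that a mean-based test is still reported after a switch.

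Continuous secondary outcomes follow the same pattern, "using an ANCOVA model or its non-parametric counterpart if the model assumptions aren't met". Under section 8.1, "statistical tests will be conducted at the 0.05 significance level (with no adjustments for multiplicity) using two-tailed tests".

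The design is a "single-center, open-label, single-arm study of 30 individuals with SSc and fatigue" (section 4.1), and section 6.2 confirms that "No randomization or blinding will occur". Section 8.1 also calls the analysis largely descriptive, treats p-values as hypothesis-generating, lists the mean, median, SD and range among the summaries, and leaves detail to a statistical analysis plan still to be written.

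**The concern.** Two defects sit in one sentence of the plan. First, the rank-sum family compares two groups and this study has one, so the fallback cannot be carried out as named. Someone will have to substitute another method once the data are in hand.

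Second, correcting the fallback to its obvious one-sample form, the signed-rank test, does not solve the problem. That test answers a question about the mean only when changes are symmetric about their centre. Marked skew is a main reason for a normality check to fail, so the switch tends to occur where the rank test and the mean part company.

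Skew is plausible here. Section 4.1.2 says "Use of the device will be entirely at the subject's control", sections 4.1.3 and 6.5 keep participants who stop using the device, and section 8.1 analyses anyone with one day of use. A minority who improve, alongside others who hardly change, would give skewed changes. At stake is whether the reported p-value belongs to the stated endpoint.

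**Working it through.** **Inputs from the plan.** One arm, n = 30, two-sided 0.05, endpoint a mean change; expected improvement about 5 and SD about 5 (Synopsis).

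**Assumed, because the plan is silent.** Fallback: Wilcoxon signed-rank on the changes. Trigger: Shapiro-Wilk p < 0.05. Shape of the changes: varied below. No dropout.

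**The plan's own power figure.** The Synopsis gives 86% for a paired t-test with effect size 1 and n = 30. The noncentrality is 1 × √30 = 5.48, and the two-sided power is 99.96%, so 86% is not reproduced. A one-sided two-group normal approximation with 15 per arm does give it: 1 × √(15/2) − 1.645 = 1.094, and Φ(1.094) = 86.3%. That is a separate matter. For this point, what counts is that with normal changes of mean 5 and SD 5 the t-test and the switch rule both have power of about 99.9%.

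**Why the target moves.** The signed-rank test is centred on the pseudo-median (the median of averages of two independent changes). Take an exponential shape shifted to mean 0 with SD 1 (skewness 2). The median m of the sum of two unit exponentials solves (1 + m)e^(−m) = 0.5, so m = 1.678. The pseudo-median is 1.678/2 − 1 = −0.16 SD although the mean is exactly 0.

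**False rejection with zero mean change** (simulation, n = 30, 6,000 to 20,000 trials per case):

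| Shape of changes | Switch rule | t-test |
|---|---|---|
| Normal | 5% | 5% |
| Gamma, skewness 1 | 7–8% | about 6% |
| Gamma, skewness 1.5 to 1.6 | 11–13% | 6–7% |
| Gamma, skewness 2 | 16% | about 7% |
| 20% at +12, the rest at −3, SD 4 | 10% | 5–6% |

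The last row has mean 0.20 × 12 − 0.80 × 3 = 0. At skewness 1.5 the rate stays at 10.6–11.3% if the trigger is Shapiro-Wilk at 0.01 or absolute sample skewness above 1. It grows with n. The Synopsis mentions "increasing the number of patients to 40" and section 8.5 allows up to 100; at skewness 1.5 the rule rejects in 12.6% of trials at n = 40 and 23.6% at n = 100.

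**Direction.** With a tail of strong decliners (skewness 1.5), 10.7 of 11.3 percentage points are false improvement. With a tail of strong improvers (last row of the table), 9.4 of 10.2 points are false worsening.

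**Power when a fraction p improves by D, the rest by 0, noise SD s.** Mean = pD; total SD = √(s² + p(1 − p)D²).

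| Case | Mean | Total SD | t-test | Switch rule |
|---|---|---|---|---|
| p = 25%, D = 20, s = 5 | 5 | √(25 + 75) = 10 | 79% | 57% |
| p = 20%, D = 15, s = 4 | 3 | √(16 + 36) = 7.2 | 60% | 42% |
| p = 1/3, D = 15, s = 5 | 5 | √(25 + 50) = 8.7 | 89% | 83% |

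The loss depends on the trigger. In the first case, a trigger of absolute sample skewness above 1 leaves power at 73%.

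**Where the switch helps.** Symmetric heavy tails (t with 3 df, effect size 0.5): t-test 81%, switch rule 92%.

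**The case against.** The strongest reply is that the signed-rank test appears nowhere in the documents. The named family is rank-sum, and on two groups of 15 drawn from the same skewed distribution it rejects at 4.3–4.7%, with no inflation. That is correct, and it means the error rates above are conditional. It does not rescue the plan, because two such groups do not exist here.

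Three further objections stand in part. The responder cases have total SDs of 7.2 to 10 against the plan's 5, and the t-test alone already misses 11% to 40% of them, so only the gap is due to the switch. A fallback triggered by non-normality is conventional, and defining the trigger while always reporting the mean with its interval would remove much of the difficulty. The p-values are hypothesis-generating, means and SDs are reported whichever test is used, and the later analysis plan could still settle the details.

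A reader might infer that the plan as written doubles the false-positive rate, or that it favours a false claim that the device works. The documents support neither. The named method cannot be run, and the skewness is unknown. If use at will produces a tail of improvers, the false rejections are almost all towards worsening; false improvement needs a few participants who worsen strongly.

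**Conclusion.** The point holds in a limited form. Two things follow from the text alone: the test is replaced on an undefined, data-driven trigger with no mean-based test retained, and the named fallback does not fit one arm. The size of the harm rests on three assumptions: a signed-rank substitute, a normality trigger, and the skewness of the changes.

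Under those assumptions the false rejection rate is little changed for a gamma shape with skewness up to about 1, nearly doubles around 1.5 and is a little more than double the t-test's at 2. Power falls by about 18 to 22 percentage points when a fifth to a quarter respond strongly, by about 6 when one third respond, and not at all in the scenario on which the plan bases its sample size. It would be wrong to conclude that the primary analysis is generally underpowered. This is a modest defect, worth correcting because the correction is cheap.

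**What to change.** In section 8.2.2, delete the switch and the rank ANCOVA text. Make the one-sample (paired) t-test of the mean change, with its 95% confidence interval, the primary analysis in all cases, and add a bootstrap interval for the mean as a check if changes are skewed. Report the signed-rank test as a labelled sensitivity analysis that does not replace the t-test. Apply the same rule to the continuous secondary outcomes, and carry it into the statistical analysis plan.

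The cost is wording only. The downside is some lost power if changes are symmetric with heavy tails, as in the 81% against 92% case; the sensitivity analysis would show this.

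### The ANCOVA named for the continuous secondary measures has no group to compare in this one-arm trial and no stated contrast, so its default p-values do not test mean change

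*Combined protocol and SAP*

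**What the plan says.** Section 6.2 is explicit: "This is an open-label, single-arm trial. No randomization or blinding will occur". The Synopsis ("Open label, single-arm, single center US study") and section 4.1 agree.

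Section 8.2.2 is nevertheless written for two groups. For the primary endpoint, "changes in score will be compared in the two treatment groups using an repeated measures t-test". The fallback extends the rank-sum test, itself a two-group method, with the remark that "This rank ANCOVA can provide additional power associated with baseline covariate adjustment".

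Two sentences cover the continuous secondary measures. The first is "Analysis for secondary outcome measures that are continuous will be performed using a similar approach as that for the primary endpoint". The second is "We will compare the change in each secondary outcome measure from baseline to week 2 using an ANCOVA model", or a non-parametric counterpart if assumptions fail. No model terms, centring, contrast or adjusted mean are given. Baseline is named as a covariate only in connection with the rank fallback.

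Section 8.1 adds that, where appropriate, "statistical tests will be conducted at the 0.05 significance level (with no adjustments for multiplicity) using two-tailed tests and p-values will be reported". It also calls the analysis largely descriptive, gives the p-values a hypothesis-generating role, and defers detail to a separate SAP still to be written.

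**The concern.** The question for each continuous secondary measure (QUIDS-SR, PROMIS-29, HAQ-DI, the SHAQ scales, Raynaud's condition score, the global assessments) is whether its mean changed. ANCOVA ordinarily answers a different question: whether two groups differ after adjustment for baseline. Without the group term, the result that the analysis was meant to deliver is gone.

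A rank-sum test cannot be run on one group, so that error shows itself. A regression of change on baseline does run and prints p-values. An analyst who follows the text would get plausible output for a hypothesis nobody asked about, on most of the secondary measures. It could flag measures with no mean change and pass over measures that did change. The two sentences on secondary measures also disagree, because the primary method they call similar is a t-test on repeated measures.

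**Working it through.** **Plan's own figure.** There is none for this analysis. The power figures in the Synopsis concern a paired t-test on the primary endpoint and play no part here.

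**Inputs from the documents.** One arm (Synopsis, 4.1, 6.2); n = 30, with an option of 40 (Synopsis); two-sided 0.05 without multiplicity adjustment (8.1).

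**Assumptions.** The documents give no correlations, means or SDs for these measures. I take normal scores and a test-retest correlation r of 0.5 to 0.9. The T-score-like scale has mean 55 and SD 7; the HAQ-like scale has mean 1.0 and SD 0.7. SDs are equal at both visits unless stated.

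**Model.** Let m be the baseline mean, d the true mean change and k the follow-up SD divided by the baseline SD. In one group:

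- Expected change at baseline x = d + (rk − 1)(x − m).
- Slope = rk − 1. With k = 1 and r = 0.7 this is −0.3, whatever the value of d.
- Uncentred intercept (x = 0) = d + (1 − rk)m. With d = 0, k = 1 and r = 0.7 it is 0.3 × 55 = 16.5 on the T-score-like scale and 0.3 × 1.0 = 0.3 on the HAQ-like scale. Neither is zero, although nothing changed on average.
- Intercept with baseline centred at the sample mean = the sample mean change. This does target d, but its standard error treats the mean baseline as fixed.

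**Analytic check, r = 0.7, k = 1.** The correlation of change with baseline is −√((1 − r)/2) = −√0.15 = −0.387, which 30 participants detect about 57% of the time. The centred-intercept standard error is too small by √(1 − 0.387²) = 0.92. The critical value is then effectively 1.96 × 0.92 = 1.80, giving about 7% error.

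**Simulation, no mean change, n = 30, equal SDs, 20,000 trials per setting. Share significant at 0.05:**

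| r | Slope | Uncentred intercept, T-score-like | Uncentred intercept, HAQ-like | Centred intercept | Paired t |
|---|---|---|---|---|---|
| 0.5 | 83% | 82% | 68% | 9% | 5% |
| 0.7 | 58% | 57% | 44% | 7% | 5% |
| 0.8 | 40% | 39% | 30% | 6% | 5% |
| 0.9 | 22% | 22% | 17% | 6% | 5% |

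At n = 40 and r = 0.7 the slope figure rises to 71%.

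**Unequal SDs.** With k = 1.2 the slope is 0.7 × 1.2 − 1 = −0.16 at r = 0.7 and 0.8 × 1.2 − 1 = −0.04 at r = 0.8. Slope rejection falls to about 16% and 6%. At k = 1/r the slope is zero and the excess vanishes.

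**Direction.** With d = 0 and k = 1 the uncentred intercept is (1 − r)m, which is positive, and its rejections are almost all positive. The slope carries no direction of mean change. A significant slope beside an observed fall in the mean occurs in about 40%, 30% and 11% of null trials at r = 0.5, 0.7 and 0.9. The paired t-test shows a significant fall in about 2.5%.

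**A real improvement.** Take a true fall of 0.5 SD at r = 0.7. The paired t-test has 93% power. The uncentred intercept is significant in 40% of trials on the T-score-like scale, where its expected value is 16.5 − 3.5 = 13.0 and so still points upwards. It is significant in 6% on the HAQ-like scale, where its expected value is 0.3 − 0.35 = −0.05.

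**The case against.** The strongest reply is that the plan never says the slope or the uncentred intercept will be reported. Adjusted mean change at the mean baseline is an ordinary way to use such a model, and under it the excess error is only 1 to 4 percentage points. Read with the preceding sentence and the Synopsis, which speaks of a paired t-test and a repeated measures model, the intention may simply be a within-person test. All of this stands, and it makes the large rates conditional on a misreading. It does not supply the missing contrast.

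A reader might infer that the plan will declare improvement on most secondary measures when nothing has changed. The documents do not support that. Null rejections of the uncentred intercept run upwards, which is worsening on scales such as the global assessments in section 7.6.4, where 10 is the worst score. The slope could become a claim of improvement only if someone read the baseline coefficient as the treatment result, and nothing in the plan says to do so.

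It is also fair that the text looks like a remnant of a two-arm trial: section 8.2.1 summarises by treatment group and section 8.5 mentions riociguat against placebo. One rewrite of 8.2.2 could settle several such points. Means and SDs will be reported and would show an absent change. The hypothesis-generating label limits the weight of any p-value, but it does not make a p-value for another hypothesis informative. The later SAP might correct this, but it is not among the documents. Nor does the non-parametric counterpart help if it is the rank ANCOVA described for the primary endpoint, since that too compares groups.

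**Conclusion.** The point holds in a limited form. As written, section 8.2.2 names a group-comparison model for a trial with one group and leaves unstated which quantity would be tested. The default slope and uncentred-intercept p-values do not test mean change. Used that way, they reject in roughly 17% to 83% of null trials over the equal-SD range examined, and the uncentred intercept can miss or reverse a real improvement. With a centred baseline the model does target mean change, at about 6% to 9% error.

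The larger figures rest on assumed correlations, means and equal SDs, and on one of the default p-values being taken as the result. They should not be read as the error rate the trial will have. The contradiction between the two sentences on secondary measures rests on no assumption. The passage should be corrected before analysis, but the consequence is confined to secondary, exploratory conclusions.

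**What to change.** In section 8.2.2, replace the ANCOVA sentence with, for example: *Change from baseline to end of study in each continuous secondary measure will be tested with a paired t-test on the within-person change, or the Wilcoxon signed-rank test if the changes are clearly non-normal, and reported with a 95% confidence interval.* If a model is preferred, use a mixed model with visit as a fixed factor and participant as a random effect, and report the visit effect. State that neither the baseline slope nor an uncentred intercept will serve as the test of change.

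While editing, reconcile the week 2 time point in this sentence with the four-week period in the Synopsis and sections 2 and 4.1.

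The cost is one sentence, with no new data or participants. Some secondary p-values will be less favourable. Against a centred ANCOVA the loss of power is small: 93% against 95% at a true 0.5-SD change and r = 0.7, and part of that 95% comes from the centred model's inflated error.

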7.3 Efficacy

Primary efficacy outcome measure:

- Change from baseline to end of study on the PROMIS-Fatigue scale.

Secondary efficacy measures during double-blind period:

- HRQOL using PROMIS-29
- Physical function as assessed by HAQ-DI, and HDIIS-DU
- Visual analog scales from scleroderma-health assessment questionnaire (SHAQ) assessing burden of digital ulcers, Raynaud's disease, gastrointestinal involvement, breathing, and overall disease
- QUIDS-SR
- Improvement of Raynaud's phenomenon
 - Raynaud's condition score
 - Number of Raynaud's attacks/day
 - Patient and physician assessment of RP; pain, numbness, and tingling during an RP attack; and duration of attacks
- Patient's and physician's global assessment on a Likert scale
-

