7.6 OTHER PROCEDURES AND VARIABLES

7.6.1 Raynaud's attacks assessment

Raynaud's attacks will be assessed using the composite of the following 6 individual outcome measures in order to minimize the measurement variability and placebo response(7): Raynaud's condition score, patient assessment of Raynaud's phenomenon, physician assessment of Raynaud's phenomenon, attack symptoms, duration of attacks, and number of attacks per day.

The Raynaud's condition score is a daily patient assessment of Raynaud's phenomenon activity using a 0-10 ordinal scale. It incorporates the cumulative frequency, duration, severity and impact of Raynaud's phenomenon attacks, reflecting the overall degree that Raynaud's has affected use of the participant's hands. The Raynaud's condition score, along with details of the frequency and duration of Raynaud's attacks, will be incorporated into the daily diary that participants will be asked to complete for 1 week (7 days) at the time points shown below.

The patient and physician assessment assesses the severity of Raynaud's phenomenon in the past week using a 0-100 VAS.

Frequency: The diary is to be completed by participant for one-day during the observation period, and one-day at the end of study (to occur the day prior to end of study visit).

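### Raynaud attack counts are to be analysed by Poisson regression with no stated allowance for extra within-person variation; if a person's attack rate shifts between diary periods, the standard error is too small.

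*Combined protocol and SAP*

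**What the plan says.** Section 8.2.2 (Efficacy) gives counts one sentence: "Analyses of secondary outcome measure that are counts will be performed using Poisson regression". It does not say how the two measurements per person enter the model, how variation beyond Poisson is checked or handled, or whether there is an offset for diary days. The same section gives the primary and continuous secondary outcomes a non-parametric fallback. Counts get none.

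The count outcome is listed in section 7.3 as "Number of Raynaud's attacks/day". The design is stated in section 4.1: "This clinical trial is a single-center, open-label, single-arm study of 30 individuals with SSc and fatigue". Section 8.1 says that "statistical tests will be conducted at the 0.05 significance level (with no adjustments for multiplicity) using two-tailed tests and p-values will be reported". It also promises more detail: "A statistical analysis plan (SAP) will be written for the study that contains detailed descriptions of the analyses to be performed".

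The diary that supplies the counts is described in two ways.

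- **Seven days.** Section 4.1 says of the observation period: "During this one week phase participants will track their daily Raynaud attack frequency and duration using a diary". Of the intervention it says: "Participants will track their daily Raynaud attack frequency and duration using a diary during week 4 of Apollo use". Sections 4.1.1 and 4.1.2 and one paragraph of 7.6.1 agree.
- **One day.** The last paragraph of section 7.6.1 says: "The diary is to be completed by participant for one-day during the observation period, and one-day at the end of study". Sections 2.1 and 7.1.2.2 also describe one-day recording.

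**The concern.** Poisson regression takes the variance of each count to equal its mean. In a before/after comparison, a person who always has many attacks contributes many to both periods, and that difference cancels in the ratio. A change in the person's own rate between the two periods (weather, activity, a flare) does not cancel, and the Poisson standard error does not contain it. The two diary periods are about a month apart, so the model needs every person's underlying rate to be the same at both times apart from any common effect.

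If that fails, the interval for the change in attack frequency is too narrow and its p-value too small. The study exists to give preliminary estimates of the size of effects (section 8.5), so an interval that overstates precision matters even where the p-value is only hypothesis-generating.

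There is a smaller related gap. The outcome is a daily rate taken from a home paper diary, yet no exposure term is stated. If totals were modelled without one, a missed diary day would read as fewer attacks.

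**Working it through.** **Inputs from the documents:** 30 participants; single arm; two-sided 5% level; diary of 7 days or 1 day per period. The plan states no mean, variance, dispersion or power for attack counts. Its power figures concern PROMIS-Fatigue, so there is no figure of its own to reproduce here.

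**Assumptions, not in the documents:** mean 1, 2 or 4 attacks per day; between-person CV 0.8; within-person period-to-period CV 0.2, 0.3 or 0.4; no true change.

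**Step 1: Poisson standard error.** With period totals S1 and S2, the standard error of log(S2/S1) is √(1/S1 + 1/S2). At 2 attacks per day and 7 days, each total is 30 × 2 × 7 = 420, which gives √(2/420) = 0.069.

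**Step 2: true variance.** Let m be the mean count per person per period. When each person's rate varies between periods with CV c_w, and people differ with CV c_b, the variance of S2 − S1 is the Poisson value times

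φ = 1 + m(1 + c_b²)c_w².

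If c_w = 0 then φ = 1, whatever c_b is. Between-person spread alone does no harm.

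**Step 3: false-positive rate.** The two-sided rate is 2[1 − Φ(1.96/√φ)], and half of it is false improvement. With c_b = 0.8, 1 + c_b² = 1.64. At 2 attacks per day:

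| Diary | m | c_w | φ | Two-sided | False improvement |
|---|---|---|---|---|---|
| 7-day | 14 | 0 | 1.00 | 5.0% | 2.5% |
| 7-day | 14 | 0.2 | 1.92 | 15.7% | 7.9% |
| 7-day | 14 | 0.3 | 3.07 | 26.3% | 13.2% |
| 7-day | 14 | 0.4 | 4.67 | 36.5% | 18.2% |
| 1-day | 2 | 0.2 | 1.13 | 6.5% | 3.3% |
| 1-day | 2 | 0.4 | 1.52 | 11.2% | 5.6% |

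**Step 4: simulation.** Gamma-Poisson counts for 30 pairs with no true change gave 15%, 26% and 35% for the three 7-day rows with c_w above 0 (false improvement about 7–17%) and 6–11% for one-day diaries. At c_w = 0 the rate was 5%. With 7-day diaries it was 10–24% at 1 attack per day and about 24–49% at 4 per day. A paired t-test on the change stayed at 4–5% throughout. A wider set of assumptions (between-person CV 1, within-person CV up to 0.5, day-to-day CV up to 0.5) gave 11–63% for 7-day and 5.8–38% for one-day diaries.

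**Step 5: effect on the interval.** In the 7-day case with c_w = 0.3, the true standard error is 0.069 × √3.07 = 0.121. Around a ratio of 1, the Poisson interval is exp(±1.96 × 0.069) = 0.87 to 1.14. The correct one is exp(±1.96 × 0.121) = 0.79 to 1.27.

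**Step 6: which repairs work.**

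- Adding person effects to the Poisson model changes nothing. In one simulated data set the standard error was 0.0731 with and without them, against a robust value of 0.255.
- A dispersion factor in a model that ignores pairing overcorrects: with between-person CV 1 and 7-day or one-day diaries, its false-positive rate was 0–2%.
- A paired Poisson model with person-clustered robust errors and t(29) gave 5.9–8.1% where extra variation was present. That is slightly high, which is why a small-sample correction is asked for.

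**Step 7: missed diary days.** Suppose totals were modelled with no offset, baseline diaries were complete and 10% of week-4 days were missing (assumed). The expected ratio is then 0.90 with no true change. With totals of 420 and 378 the standard error is √(1/420 + 1/378) = 0.071, and log(0.90)/0.071 = −1.49. The chance of falling below −1.96 is Φ(−0.47), about one in three.

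**The case against.** The documents contain no data on attack counts, so extra-Poisson variation within a person is an assumption and every rate above depends on chosen values. That stands, and the point is therefore conditional. The plan does lean the same way: section 7.6.1 adopts a six-part Raynaud composite partly to reduce measurement variability.

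Section 8 is a summary and a detailed SAP is promised. One sentence naming a model family does not rule out a scale parameter, robust errors or an offset. That also stands: the missing offset is inferred from silence, and missed days at baseline would bias the result against the device. But Poisson regression is the only method stated for counts, with no fallback, and no fuller SAP is among the documents.

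A reader might infer that pairing itself makes the standard error too small. It does not: with between-person spread only, the Poisson test holds its 5% level.

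If the one-day diary is the operative one, the inflation is modest. That is true, and the documents do not settle which applies.

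Finally, section 8.1 calls the analysis largely descriptive, and attack number is one of six components of the Raynaud composite. This limits the consequence but does not make the interval right.

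**Conclusion.** The point holds in conditional form. The stated method has no provision for a person's attack rate shifting between diary periods. If it does shift, the standard error is too small, and the longer the diary or the higher the attack rate, the worse the error. Under the assumptions listed, the two-sided false-positive rate is about 15–35% with 7-day diaries and about 6–11% with one-day diaries at 2 attacks a day.

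A reader might go further and conclude that a false finding of improvement is likely. The figures do not support that. The errors fall in both directions, so false improvement is about 7–17% in the main 7-day case and at most 31% in the widest scenario examined, against 2.5% nominal. It is inflated, but never more likely than not.

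Severity is moderate. The primary endpoint is untouched, and the p-values are declared hypothesis-generating.

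**What to change.** Replace the sentence on counts in section 8.2.2 with:

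> For each participant compute attacks per completed diary day in each diary period and analyse the within-person change by paired t-test, with the Wilcoxon signed-rank test as sensitivity. If a rate ratio is reported, use a Poisson model clustered on participant with small-sample-corrected robust standard errors and log(completed diary days) as offset.

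The paired t-test should lead because it held its level in every setting simulated. The small-sample-corrected version of the clustered model was not itself simulated.

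Two consistency repairs belong with it. Reconcile the 7-day diary (sections 4.1, 4.1.1, 4.1.2 and part of 7.6.1) with the one-day diary (sections 2.1, 7.1.2.2 and the rest of 7.6.1), since the size of the error depends on it. In section 8.2.2, reconcile the comparison of two treatment groups and the two-week time point with the single-arm, four-week design in the Synopsis and section 4.1.

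The cost is a few lines of text and no new data. The interval for attack frequency will be wider wherever extra variation is present.
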